PILOT PHASE II MULTICENTER STUDY OF THE PI3K INHIBITOR COPANLISIB IN COMBINATION WITH A KETOGENIC DIET IN THE TREATMENT OF PATIENTS WITH RELAPSED OR REFRACTORY FOLLICULAR LYMPHOMA OR ENDOMETRIAL CANCER

NCT04750941

Protocol date: 9/23/2024

PROTOCOL SYNOPSIS

Study Design: This is a multi-institution, open label, pilot phase II study of the PI3K inhibitor copanlisib in combination with a ketogenic diet in the treatment of patients with one of the following malignancies: (a) relapsed or refractory (R/R) follicular lymphoma (FL), (b) R/R endometrial cancer (EC) with a documented activating mutation in PIK3CA or loss of PTEN. The FL arm will enroll 23 subjects and the EC arm will enroll 19 subjects. The study will be stopped if the safety trigger is activated at the pre-specified times of interim safety analysis upon enrollment of 12 and 24 patients.

The two arms will enroll patients in parallel and independently. Safety analysis will be done by pooling patients from the two arms together. Efficacy analysis will be conducted independently within each arm.

Objectives: Primary Objectives

- Determine the objective response rate (ORR) (complete response [CR] + partial response [PR]) in FL.
- Determine the ORR in EC.

Secondary Objectives:

- Determine the CR and PR rates in FL upon completion of the study protocol.
- Determine the CR and PR rates in EC upon completion of the study protocol.
- Determine the ORR in FL and EC at the Simon stage I analysis
- Determine patient compliance with the ketogenic diet.

Exploratory Objectives:

- Determine the PD markers including *blood* levels of insulin, c-Peptide, BHB (beta-hydroxybutyrate), triglyceride, and glucose, and urine ketones.
- Determine the PD markers including levels of pINSR, INSR, pAKT, AKT, pS6, S6, Ki-67, TUNEL, caspase, and actin in paired pre- and post-treatment *tumor* tissues in patients who consented for the optional post-treatment biopsy of the tumors (blood and bone marrow are acceptable if they are known to be involved by lymphoma).
- Explore the correlation of disease response and the PD markers described above.
- Explore the correlation of disease response and gene alternations in tumor tissues.
- Explore the correlation of insulin response and gene alternations in normal buccal fibroblasts.
- Determine the change in body weight and body mass index (BMI) over time.
- Determine the change in computed tomography-based body composition metrics including

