measures of adipose tissue and skeletal muscle.

• Determine the change in ¹⁸F-fluorodeoxyglucose uptake/PET-based adipose tissue and skeletal muscle peak standardized uptake value.

Target Population:

(a) R/R FL, (b) R/R EC with a documented activating mutation in PIK3CA or loss of PTEN.

Inclusion Criteria:

- Be willing and able to provide written informed consent for the trial.
- Be \geq 18 years of age on day of signing informed consent.
- For lymphoma, patients should have measurable disease based on the Lugano Criteria (Cheson et al., 2014).
- For FL patients must have received at least two lines of prior therapy. There is no upper limit for the number of prior therapies. Tumor tissues of all patients are encouraged to be submitted (optional) prospectively for whole or targeted exome sequencing of key cancer related genes, using the Columbia Combined Cancer Panel (CCCP) or a comparable sequencing platform, such as the MSK-IMPACT 468-gene oncopanel. However, the results of tumor sequencing by themselves are not inclusion criteria for FL. The test should be submitted as per standard of care; however, if the coverage is denied by patients' insurance plans the test will be waivered or if possible paid for by the research protocol.
- For EC the patients must have recurrent/advanced tumor for which surgical or the systemic curative treatments, or standard therapeutic approaches are not available. The following histologic subtypes are eligible: endometrioid, serous, clear cell, undifferentiated/de-differentiated, mucinous, squamous, transitional, not-otherwise specified, and mixed cell-type. EC must have PI3K pathway activation confirmed in mutational profiling using the MSK-IMPACT 468-gene oncopanel or an equivalent platform, as defined below:
 - (1) Genomic alteration resulting in loss of PTEN function including a) whole or partial gene deletion, frame shift mutations, or non-sense mutations. Missense mutations in PTEN will not be considered qualifying; OR
 - (2) A previously characterized activating mutation in any component of the pathway including: PIK3CA, AKT1, PIK3R1, PIK3R2, and mTOR.

However, EC must NOT have a known concurrent activating RAS/RAF mutation or loss of function alternation in NF1 of NF2 resulting in MAP kinase pathway activation.

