Dose Modification of copanlisib is described in Section 6.6.

Duration of Treatment:

Patients will be treated until one of the following events: disease progression, unacceptable adverse event(s), withdrawal of consent, general or specific changes in the patient's condition that render the patient unacceptable for further treatment in the judgment of the investigator.

Sample Size and Statistical Consideration:

The study will enroll 42 patients. The two arms will enroll patients in parallel and independently. Safety analysis will be done by pooling patients from the two arms together. Efficacy analysis will be conducted independently within each of the two arms (lymphoma, solid tumor).

Patients who do not complete the planned cycle 2 cycles of treatment, which is required for the first evaluation of response, will be replaced.

(a) The lymphoma arm will enroll 23 patients with FL.

- Simon's two-stage design (Simon, 1989) will be used. The null hypothesis that the true ORR rate is 41% will be tested against a one-sided alternative. In the first stage, 13 patients will be accrued. If there are 5 or fewer ORRs (**To be assessed after completing 4 cycles of the treatment**) in these 13 patients, the study will be stopped for futility. Otherwise, 10 additional patients will be accrued for a total of 23. The null hypothesis will be rejected if 14 or more ORRs are observed in 23 patients. This design yields a type I error rate of 5% and power of 80% when the true ORR rate is 67%. Assuming that the CR rate is 0.09 (2 out 23), with 23 subjects we will have 80% power to claim that the true CR is at least 30%.
- The reference range of ORR in FL is 40% (n = 16. Dreyling et al, Ann Oncol. 2017) to

59% (n = 104. Dreyling et al, J Clin Oncol. 2017).

• The reference CR rate is 14% (n = 104. Dreyling et al, J Clin Oncol. 2017).

(b) The solid tumor arm will enroll 19 patients with EC.

Simon's two-stage design (Simon, 1989) will be used. The null hypothesis that the true ORR rate is 0.10 will be tested against a one-sided alternative. In the first stage, 11 patients will be accrued. If there are 1 or fewer ORRs (To be assessed after completing 4 cycles of treatment) in these 11 patients, the study will be stopped for futility. Otherwise, if >=2/11 responses are observed, then 8 additional patients will be accrued for a total of 19. The null hypothesis will be rejected if 4 or more ORRs are observed in

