19 patients. This design yields a type I error rate of 10% and power of 81% when the true ORR rate is 30%.

Safety:

Patients will be monitored carefully for the development of adverse events (AEs). AE will be evaluated according to criteria outlined in the National Cancer Institute (NCI) Common Terminology Criteria for Adverse Events (CTCAE), version 5.

Safety Trigger

There will be ongoing safety monitoring.

Interim safety analysis will be performed upon enrollment of 12 and 24 subjects. Safety analysis will be done by pooling patients from the two arms together.

The safety trigger will be activated if any of the following Safety Trigger Events (STE) happens during the first cycle of treatment:

- During the interim analysis of the first 12 subjects: 3 incidents of STE excluding mortality, or 2 incidents of mortality deemed not likely to be due to progression of the cancer but possibly related to the treatment. The study will be stopped.
- During the interim analysis of the first 24 subjects: 5 incidents of STE excluding mortality, or 3 incidents of mortality deemed not likely to be due to progression of the cancer but possibly related to the treatment. The study will be stopped.

Safety Trigger Events (STE) will defined as the following:

- Any non-hematologic toxicity grade 3-4 that require delay of treatment by more than 7 days despite optimal management.
 - Note that a patient who experiences a STE may be allowed to continue the study, as long as the patient can safely resume therapy within 21 days.
- Any hematologic toxicity grade 3-4 that require delay of treatment by more than 7 days despite optimal management including blood products and growth factors.
 - Note that a patient who experiences a STE may be allowed to continue the study, as long as the patient can safely resume therapy within 21 days.

• Any mortality.

Efficacy Outcome:

Patients will be monitored for clinical and/or radiographic evidence of disease response. Response will be evaluated using clinical parameters, CT or PET/CT scan (PET/CT scan is preferred), and bone marrow or other tissue biopsy (when applicable for lymphoma), according to the Updated Recommendations for Evaluation, Staging, and Response Assessment for Hodgkin and Non-Hodgkin Lymphoma: The Lugano Classification. For solid tumor the response will be determined in accordance with the revised Response Evaluation Criteria in Solid Tumors

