(RECIST) guideline. CT or PET/CT scan will be performed after every two 28-day cycles of. After cycle 4, if the patient has achieved CR, scans will be done every 3 cycles.

Data analysis:

All patients receiving at least one dose of copanlisib will be evaluable for toxicity and all patients completing at least one 28-day cycle of therapy (copanlisib plus ketogenic diet) will be evaluable for response and time-to-endpoint analyses.

Response will be estimated with exact 95% confidence intervals (CIs). We will estimate overall survival, progression-free survival, and duration of response using the Kaplan-Meier method. Group comparisons, between groups associated with different biomarkers described below, will be made using a two-sided log-rank test, and the estimated hazard ratios and 95% CIs will be calculated using Cox regression. Overall survival will be assessed post hoc in the trial patients. In the exploratory correlative biomarker analyses, any patients with assessable biological samples (blood, tumor etc) will be included. An association between disease outcome (complete response, partial response, stable disease, progression of disease, duration of response, and progression-free survival) and changes from baseline in biomarker concentrations as a function of treatment over time will be assessed. Because of sample size considerations, we will base group comparisons for these analyses on two-sample t test. We will do correlative studies including all enrolled patients that have adequate biological samples available for analysis. We plan to assess changes over time and estimate odds ratios using mixed-effects logistic regression models or a linear model if the sample sizes for comparison are too small. We will summarize continuous variables as means and SDs, and categorical variables as counts with percentages. We will not do multiple testing adjustments. All the analyses will be done with SAS version 9.4.

Study Rationale

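### Endometrial cancer (EC) eligibility does not require measurable disease, although the arm's primary endpoint is ORR by RECIST; a patient without a measurable lesion could respond only through CR yet would stay in the denominator

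*Combined protocol and SAP*

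**What the plan says.** **Eligibility.** In the Protocol Synopsis, Inclusion Criteria, measurability is tied to one disease: "For lymphoma, patients should have measurable disease based on the Lugano Criteria". The EC entry reads "For EC the patients must have recurrent/advanced tumor for which surgical or the systemic curative treatments, or standard therapeutic approaches are not available", and then lists the eligible histologies and the qualifying PI3K-pathway alterations. No other inclusion or exclusion criterion mentions measurable disease for EC.

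**Endpoint.** The first primary objective is "Determine the objective response rate (ORR) (complete response [CR] + partial response [PR]) in FL"; the second is "Determine the ORR in EC". Under Efficacy Outcome, "For solid tumor the response will be determined in accordance with the revised Response Evaluation Criteria in Solid Tumors".

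**Who is counted.** Under Data analysis, "all patients completing at least one 28-day cycle of therapy (copanlisib plus ketogenic diet) will be evaluable for response". Under Sample Size and Statistical Consideration, "Patients who do not complete the planned cycle 2 cycles of treatment" are to be replaced. Neither rule refers to lesions at baseline.

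**Design.** For EC, "The null hypothesis that the true ORR rate is 0.10 will be tested against a one-sided alternative". The first stage has 11 patients, and the arm stops with 1 or fewer responses. Otherwise 8 more are enrolled, for 19 in all, and the null is rejected with 4 or more responses. The stated type I error is 10%, and the stated power is 81% at a true ORR of 30%.

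**The concern.** A RECIST partial response is ordinarily a percentage fall in the summed diameters of target lesions chosen from measurable disease at baseline. A patient with no such lesion cannot be assigned PR, so one of the two routes to counting as a responder is closed before treatment starts. The lymphoma arm is protected against this by its own criterion; the EC arm is not.

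Nothing later in the plan repairs the gap. An EC patient without a measurable lesion who completes two cycles is evaluable, is not replaced, and occupies one of the 11 or 19 places. In an arm that stops at 1 of 11, one place can decide whether enrolment continues, and a futility stop is not easily undone. What is at stake is a missed effect in EC.

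**Working it through.** **Inputs from the documents** (Sample Size and Statistical Consideration, part b): stage 1 n = 11, continue with 2 or more responses; stage 2 adds 8; reject with 4 or more of 19; null rate 0.10; target rate 0.30.

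**Inputs assumed.** f is the share of enrolled EC patients without a measurable lesion, taken as 5% to 20% because the documents give no figure. The ORR is 30% in measurable EC and about 0 otherwise; the second value is relaxed below.

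**Step 1: reproduce the stated design.** With X1 ~ Bin(11, p) and X2 ~ Bin(8, p),

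P(reject) = sum over x = 2 to 11 of P(X1 = x) × P(X2 ≥ max(0, 4 − x)).

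At p = 0.30:

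- Early stop: 0.7^11 + 11 × 0.3 × 0.7^10 = 0.0198 + 0.0932 = 0.113.
- x = 2: 0.1998 × P(X2 ≥ 2) = 0.1998 × 0.7447 = 0.1488.
- x = 3: 0.2568 × P(X2 ≥ 1) = 0.2568 × 0.9424 = 0.2420.
- x ≥ 4: 1 − 0.1130 − 0.1998 − 0.2568 = 0.4304, always rejects.
- Power: 0.1488 + 0.2420 + 0.4304 = 0.821.

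At p = 0.10 the same sum gives 0.0988. The stated 81% and 10% are therefore reproduced to within rounding or about one point.

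**Step 2: dilute the response rate.** Replace p by p × (1 − f) and repeat. The last column applies the same dilution to the 10% null rate.

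| f | Expected patients of 19 | Effective rate | Power | Early stop | Type I error |
|---|---|---|---|---|---|
| 0 | 0 | 0.300 | 82.1% | 11.3% | 9.9% |
| 5% | 0.95 | 0.285 | 78.5% | 13.4% | 8.5% |
| 10% | 1.9 | 0.270 | 74.5% | 15.9% | 7.3% |
| 20% | 3.8 | 0.240 | 64.8% | 21.9% | 5.1% |

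**Step 3: count patients instead of shares.** With exactly one such patient in stage 1, X1 ~ Bin(10, 0.30).

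- Early stop: 0.7^10 + 10 × 0.3 × 0.7^9 = 0.0282 + 0.1211 = 0.149.
- Power: 0.2335 × 0.7447 + 0.2668 × 0.9424 + 0.3504 = 0.1739 + 0.2514 + 0.3504 = 0.776.

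If the one patient falls in stage 2 instead, power is 80.0% and the early-stop chance is unchanged. Two in stage 1 give power of 72.0% and early stopping of 19.6%; one in each stage gives power of 75.2%.

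**Step 4: allow some CRs.** If a patient without a measurable lesion has an assumed 5% chance of CR, the effective rate is 0.30 × (1 − f) + 0.05 × f. That is 0.275 at f = 10% and 0.250 at f = 20%. Power is then 75.9% and 68.2%, so the loss shrinks but does not disappear.

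**The case against.** Several points on the other side are sound.

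- **CR still counts.** A reader might infer that EC patients without measurable disease are bound to be scored as non-responders. The documents do not say so. ORR includes CR, and the plan does not state how such a patient is classified. What can be said is that only the PR route is closed.
- **RECIST is cited, not reproduced.** The plan defines neither PR nor target lesion, so the mechanism rests on the usual reading of the guideline. The guideline may also say something about entry to trials with a response endpoint. The plan does not invoke it for eligibility, and for lymphoma it wrote the requirement out.
- **The public text is a synopsis.** It points to Sections 5.6 and 6.6 and Appendix 5, which are not in it. Those references concern withdrawal, dose modification and angina class. The eligibility list reads as complete, but a rule elsewhere in the full protocol cannot be excluded.
- **The size is conditional.** No document gives the share, and nothing shows that any such patient was enrolled. A single such patient costs about 2 to 5 points of power (82.1% to 80.0% or 77.6%).
- **The 10% and 30% have no stated source population.** Reference rates are cited for FL only. If 30% is meant as the rate in everyone the EC criteria admit, the stated power is unaffected. The losses above apply if 30% is the rate in patients with measurable disease.
- **The error is conservative.** It cannot produce a false claim of efficacy.

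These points limit the size and certainty of the concern. They do not supply the missing EC criterion, and in a multi-institution trial uniform site practice cannot be assumed.

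**Conclusion.** The gap is real in the current text: measurable disease is required for lymphoma and not for EC, while the EC primary endpoint depends on RECIST response. Under the evaluability and replacement rules, an EC patient without a measurable lesion who completes two cycles stays in the denominator and can contribute a response only through CR.

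The consequence is possible loss of power and more false futility stops. Under the stated assumptions, power falls by about 4 points at a 5% share (82.1 − 78.5 = 3.6) and about 17 points at 20% (82.1 − 64.8 = 17.3). Type I error falls rather than rises. Two stronger inferences are not supported: that the stated Simon figures are wrong (they reproduce), and that the EC result is already biased (no enrolment data are given). Confidence is moderate as to size, because the share is unknown. This is a cheap improvement that should be made, not a defect that invalidates the design.

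**What to change.** Add to the EC inclusion criteria: at least one measurable lesion per RECIST on the baseline CT, or on the CT part of the PET/CT.

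If any EC patient without such a lesion is already enrolled, keep that patient in the planned analysis. Also report EC ORR among patients with measurable baseline disease, labelled as a supplement.

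The sample size, stage boundaries and design error rates stay as they are. The check uses the baseline scan that response assessment needs anyway. The cost is one eligibility line in an amendment, and a few EC patients with only non-measurable disease would no longer be eligible.

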^f If not on target, this evaluation may be repeated once after at least 24 hours either according to the MDRD abbreviated formula or by 24 hour sampling. If the latter result is within acceptable range, it may be used to fulfill the inclusion criteria instead.

Exclusion Criteria:

- The following treatments are prohibited: (a) Chemotherapy (including PI3K inhibitors and other approved or investigational drugs) and monoclonal antibody within 3 weeks; (b) radiotherapy within 2 weeks prior to entering the study; (c) systemic steroids that have not been stabilized (≥ 5 days) to the equivalent of ≤10 mg/day prednisone prior to the start of the study drugs.
- Patients that have not recovered from adverse events due to chemotherapy agents administered more than 3 weeks earlier.
- Hypersensitivity to copanlisib or any of its excipients.
- Type I diabetes
- Uncontrolled Type II diabetes mellitus (HbA1c>7.5%).
- Type II diabetes requiring treatment with a sulfonylurea, meglitinide, or insulin.
- Patients that received major surgery and have not recovered adequately from the toxicity

and/or complications from the intervention prior to starting therapy.

- Patients with active, clinically serious infections > CTCAE version 5 Grade 2.
- Patients with known active concurrent malignancy with the following exception: nonmelanoma skin cancer, prostatic intraepithelial neoplasia, or carcinoma *in situ* of the cervix, prostate cancer that responds to androgen deprivation therapy and has no progression of disease for at least 12 months. If there is a history of prior malignancy, the patient must be disease-free for \geq 3 years.
- Uncontrolled hypertension, *i.e.*, blood pressure (BP) of \geq 150/90; patients who have a history of hypertension controlled by medication must be on a stable dose (for at least one month) and meet all other inclusion criteria.
- Concomitant use of strong CYP3A4 inhibitors.
- Uncontrolled moderate to severe hypertriglyceridemia (TG>300 mg/dL).
- Myocardial infarction within 6 months of cycle 1, day 1. [Subjects with a history of myocardial infarction between 6 and 12 months prior to cycle 1, day 1, who are asymptomatic and have had a negative cardiac risk assessment (treadmill stress test, nuclear medicine stress test, or stress echocardiogram) since the event, may participate].

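### FL arm: the visible text lets a patient's only measured lesion be one still shrinking after radiotherapy, and that shrinkage would count toward the primary response rate.

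*Combined protocol and SAP*

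**What the plan says.** **Radiotherapy.** The Exclusion Criteria in the Protocol Synopsis bar "radiotherapy within 2 weeks prior to entering the study". This is a time window that applies to the patient. It carries no condition on which lesion was treated, and no other radiotherapy limit appears in the visible text.

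**Measurable disease.** The Inclusion Criteria state: "For lymphoma, patients should have measurable disease based on the Lugano Criteria". They say nothing about irradiated sites or growth since irradiation. The relapsed-or-refractory condition and the requirement of two prior lines describe the patient, not the lesion that will be measured.

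**Endpoint.** The primary FL objective is: "Determine the objective response rate (ORR) (complete response [CR] + partial response [PR]) in FL". The Efficacy Outcome section cites the Lugano Classification for response and does not reproduce its rules. Scans follow every two cycles. No timing of the baseline scan relative to earlier radiotherapy is visible.

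**Test.** Sample Size and Statistical Consideration (a) sets a Simon two-stage design against a null response rate of 41%. The arm stops for futility at 5 or fewer responses in 13. At the end, "The null hypothesis will be rejected if 14 or more ORRs are observed in 23 patients". The stated operating characteristics are 5% type I error and 80% power at a true rate of 67%.

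**The concern.** A lesion irradiated shortly before entry may still be shrinking when study treatment starts. If it is the patient's only measurable lesion, the response call rests on it alone. A fall in size or uptake is then credited to copanlisib plus diet, whatever caused it.

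The bias runs in one direction, because carry-over from radiotherapy can add responses but not remove them. A randomized comparison would share the effect between arms. Here the count is compared with a fixed 41%, so every borrowed response goes straight into the test statistic. The same count drives the stage 1 futility decision, so a borrowed response can also keep an inactive combination going.

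**Working it through.** **Inputs** (Sample Size and Statistical Consideration (a)): n1 = 13, continue if 6 or more respond; n2 = 10; total 23, reject if 14 or more respond; p0 = 0.41; p1 = 0.67.

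**Step 1. Reproduce the plan's figures.** The exact rejection probability is

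P(reject | p) = sum over x = 6 to 13 of P(X1 = x) × P(X2 ≥ 14 − x), with X1 ~ Bin(13, p) and X2 ~ Bin(10, p).

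At p = 0.41:

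| x in stage 1 | P(X1 = x) | P(X2 ≥ 14 − x) | product |
|---|---|---|---|
| 6 | 0.2029 | 0.0146 | 0.00296 |
| 7 | 0.1410 | 0.0626 | 0.00882 |
| 8 | 0.0735 | 0.1834 | 0.01348 |
| 9 | 0.0284 | 0.3922 | 0.01112 |
| 10 | 0.0079 | 0.6425 | 0.00507 |
| 11 to 13 | | | 0.00145 |

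The sum is 0.0429. At p = 0.67 the same formula gives 0.8006. The stated 5% (read as a ceiling) and 80% are both reproduced.

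**Step 2. One certain radiotherapy-driven responder, everyone else at the null.**

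- In stage 1: X1 ~ Bin(12, 0.41), continue if X1 + 1 ≥ 6, reject if X1 + 1 + X2 ≥ 14. The result is 0.0664.
- In stage 2: X1 ~ Bin(13, 0.41), X2 ~ Bin(9, 0.41), reject if X1 + X2 + 1 ≥ 14. The result is 0.0658.

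Both round to 6.6%. In the stage 1 case, the chance of stopping early under the null also falls, from P(Bin(13, 0.41) ≤ 5) = 0.545 to P(Bin(12, 0.41) ≤ 4) = 0.410.

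**Step 3. A chance of carry-over instead of a certainty.** Let c be the chance that a patient who would not otherwise respond is counted as a responder because of earlier radiotherapy. The effective null rate is p = 0.41 + 0.59c, put into the Step 1 formula. The expected number of borrowed responses in 23 patients is 23 × 0.59 × c. The values of c are assumptions; the documents give none.

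| c | effective p | expected borrowed responses | type I error |
|---|---|---|---|
| 0 | 0.4100 | 0 | 4.3% |
| 1% | 0.4159 | 0.14 | 4.9% |
| 2% | 0.4218 | 0.27 | 5.5% |
| 5% | 0.4395 | 0.68 | 7.7% |

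The stated 5% is passed somewhere between c = 1% and c = 2%. For scale, c is the share of patients whose only measurable lesion was recently irradiated, multiplied by the chance that such a lesion yields a radiotherapy-driven response. One such patient in 23 (4.3%) with an assumed even chance gives c = 0.5/23 = 2.2%.

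**The case against.** **The cited criteria may already settle it.** Measurability and response are both delegated to Lugano. If Lugano restricts irradiated lesions, following the protocol would include following that restriction. Neither its text nor that of RECIST is reproduced, so this cannot be checked. The public document also points to sections that are not shown (5.6, 6.6 and Appendix 5), and an imaging rule may exist elsewhere in the full protocol. This objection stands as a limit on scope. A reader might infer that nothing in the trial prevents an irradiated target lesion. The documents support only that nothing in the visible text does.

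**The endometrial arm looks more exposed.** Its rejection threshold is only 4 of 19, and its Inclusion Criteria contain no measurable-disease line, so a reader might infer a larger inflation there. That inference needs such a lesion to be accepted as a target, and the plan leaves target selection to the guideline it cites: "For solid tumor the response will be determined in accordance with the revised Response Evaluation Criteria in Solid Tumors". Without that text, an error figure for this arm would rest on a premise that the documents do not supply.

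**The scenario may be rare.** It needs recent radiotherapy outside the two-week window, no other measurable lesion, enough later regression for a response, and a patient who would not have responded anyway. The six or seven days of diet run-in may also lengthen the gap before the first copanlisib dose, depending on when entry is counted. All of this is fair. At c = 1% the error stays at 4.9%, below the stated level, so a reader should not infer that control of the type I error is lost as a matter of course.

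What remains is that the eligibility text admits the case and no visible rule says how to score it.

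**Conclusion.** The concern holds for the FL arm, as a gap in the visible eligibility and response text. A patient whose sole measurable lesion is still regressing after radiotherapy can enter and be counted in the primary response rate, with no control arm to absorb the effect.

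Its size is conditional. The 6.6% figure assumes one responder who is certain and due to radiotherapy, with all other patients at the null. The 4.9%, 5.5% and 7.7% figures assume that c applies independently and equally to every patient. Neither is an estimate of what will happen, since the frequency of recent radiotherapy is not in the documents. The conclusion also assumes that neither the cited Lugano criteria nor a section not shown already excludes such lesions. The design arithmetic itself is sound. The point is worth acting on because the bias is one-directional, the FL margin below 5% is narrow, and the remedy is small.

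**What to change.** Leave the radiotherapy washout, the sample size and the two-stage boundaries unchanged. Add to FL eligibility and to the FL response assessment:

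- at least one measurable lesion must be unirradiated, or must have documented growth since it was irradiated;
- any other irradiated lesion is followed for progression but is not used as a target lesion.

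If the full protocol or the cited Lugano criteria already contain such a rule, restating it in the synopsis is enough, and helps sites in a multicenter study to apply it alike.

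The cost is one or two sentences. The small downside is that the few patients whose only measurable lesion was recently irradiated must show growth in it before they can enter.
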